## **9. DISEASE EVALUATION AND METHODS**

### **9.1.1 Tumor Imaging**

Initial tumor imaging should be performed within 28 days prior to the start of durvalumab and every 8 weeks thereafter, or sooner if clinically indicated. A CT scan with IV and oral contrast of the chest, abdomen, and pelvis is required for initial tumor imaging and for all subsequent imaging. MRI scans are not permitted on this study.

The investigator must review baseline images to confirm the subject has measurable disease per RECIST 1.1. Subsequent images must also be reviewed for determination of treatment response. Subjects who have disease control following completion of 12 months of treatment or subjects who are withdrawn from durvalumab treatment for reasons other than confirmed PD will continue to have objective tumor assessments (see Appendix B).

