### **4.3 Withdrawal of Subjects from Study Treatment and/or Study**

#### **Permanent discontinuation of durvalumab**

An individual subject will not receive any further investigational product if any of the following occur in the subject in question:

1. Withdrawal of consent or lost to follow-up
2. Adverse event that, in the opinion of the investigator or the sponsor, contraindicates further dosing
3. Subject is determined to have met one or more of the exclusion criteria for study participation at study entry and continuing investigational therapy might constitute a safety risk
4. Pregnancy or intent to become pregnant
5. Any AE that meets criteria for discontinuation as defined in Section 6.6
6. Grade  $\geq 3$  infusion reaction
7. Subject noncompliance that, in the opinion of the investigator or sponsor, warrants withdrawal; e.g., refusal to adhere to scheduled visits
8. Initiation of alternative anticancer therapy including another investigational agent
9. Confirmation of PD and investigator determination that the subject is no longer benefiting from treatment with durvalumab

Subjects who are permanently discontinued from further receipt of investigational product, regardless of the reason (withdrawal of consent, due to an AE, other), will be identified as having permanently discontinued treatment.

Subjects who are permanently discontinued from receiving investigational product will be followed for safety per Section 10.3.1 and Appendix B or C, including the collection of any protocol-specified blood specimens, unless consent is withdrawn or the subject is lost to follow-up or enrolled in another clinical study. All subjects will be followed for survival. Subjects who decline to return to the site for evaluations will be offered follow-up by phone every month as an alternative.

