### **8.1.3 End of Treatment**

End of treatment is defined as the last planned dosing visit within the 12-month dosing period. For subjects who discontinue durvalumab prior to 12 months, end of treatment is considered the last visit where the decision is made to discontinue treatment. All required procedures may be completed within  $\pm 7$  days of the end of treatment visit. Repeat disease assessment is not required if performed within 28 days prior to the end of treatment visit.

Assessments for subjects who have completed durvalumab treatment and achieved disease control, or have discontinued durvalumab due to toxicity in the absence of confirmed progressive disease are provided in APPENDIX B.

Assessments for subjects who have discontinued durvalumab treatment due to confirmed PD are presented in APPENDIX C.

All subjects will be followed for survival until the end of the study regardless of further treatments, or until the sponsor ends the study.

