### **11.3 Determination of Sample Size**

The efficacy result will be summarized as a median PFS with a 1-sided 95% confidence interval. We will use a 1-sided test with a 5% significance level ( $\alpha$ ) to test the uni-directional hypothesis that the median PFS is prolonged from 3 to 4.5 months by combining RT combined with durvalumab in metastatic pancreas cancer patients who have progressed through first-line chemotherapy. With a statistical power ( $1-\beta$ ) of the study of 80%, we estimate an accrual time of 26 months for a total sample size of 39 patients. No early stopping rule for futility is planned due to the relatively rapid enrolment of patient in relation to the expected median PFS. The method used for sample size estimation assumes exponential survival distributions according to Dixon and Simon (Dixon et al. 1988)

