## APPENDIX B

### Schedule of study procedures: follow-up for subjects who have completed durvalumab treatment and achieved disease control (until confirmed progression of disease) and subjects who have discontinued durvalumab due to toxicity in the absence of confirmed progression of disease

Evaluation	Time Since Last Dose of durvalumab							
	Day ( $\pm 3$ )	Months ( $\pm 1$ week)						12 Months and Every 6 Months ( $\pm 2$ weeks)
	30	2	3	4	6	8	10	
Physical examination a	X							
Vital signs (temperature, respiratory rate, blood pressure, pulse)	X							
Weight	X							
AE/SAE assessment	X	X	X					
Concomitant medications	X	X	X					
ECOG performance status	X	X	X					
Subsequent anti-cancer therapy	X	X	X	X	X	X	X	X
Survival status (phone call or email)	X	X	X	X	X	X	X	X (every 2 months)
Hematology	X	X	X					
Serum chemistry	X	X	X					
Thyroid function tests (TSH, and fT3 and fT4) b	X							
CA 19-9	X							
Blood for correlative studies	X							
Blood for Future Biomedical Research	X							
Patient questionnaire (patient reported outcomes) c and health resource use	X		X					
Tumor assessment (CT)	Every 2 months							

Clinical Study Protocol

Investigational Drug Substance: MEDI4736

Study Number **ESR 15 11078**

[figure not shown]
Edition Number **1.09**

Date **01 Feb 2018**

- a Full physical exam
- b Free T3 and free T4 will only be measured if TSH is abnormal. They should also be measured if there is clinical suspicion of an adverse event related to the endocrine system.
- c For patient questionnaires different approaches based on indication and study design

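### Patients who stop durvalumab for reasons other than completion, toxicity or confirmed progression fit neither follow-up schedule, so they can lose CT and have their PFS lengthened

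*Combined protocol and SAP*

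**What the plan says.** **Who keeps being scanned.** Section 9.1.1 (Tumor Imaging) states that "subjects who are withdrawn from durvalumab treatment for reasons other than confirmed PD will continue to have objective tumor assessments", with a pointer to Appendix B. Section 9.1.3 repeats this, and Section 10.3.1 assumes it when it sets the period for collecting serious adverse events.

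**Who has a schedule.** Section 8.1.3 describes the Appendix B population as patients who completed treatment with disease control, "or have discontinued durvalumab due to toxicity in the absence of confirmed progressive disease are provided in APPENDIX B". Section 13.2 repeats this. The Appendix B heading, also shown in the list of appendices, names completers and "subjects who have discontinued durvalumab due to toxicity in the absence of confirmed progression of disease". Appendix B has a CT row (every 2 months). Appendix C is headed for confirmed progression and has no tumor assessment row.

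**Who else can stop.** Section 4.3 lists further reasons for permanent discontinuation. One is "Initiation of alternative anticancer therapy including another investigational agent"; others are noncompliance, an exclusion criterion found to have been met at entry, and pregnancy. It sends everyone who stops to Appendix B or C without saying which applies to these patients, and it follows all subjects for survival. Withdrawal of consent ends all observation.

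**How PFS is counted.** Section 11.4 ends PFS at the first documented RECIST 1.1 progression or death. It censors patients alive without disease at last contact. It has no rule for missing scans.

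**The concern.** The text describes the patients who continue CT after durvalumab in two ways, and the narrower description is the one attached to the schedules that site staff work from. A patient who stops for one of the other reasons without progression on any scan may therefore get no further CT.

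For such a patient progression can go unseen, yet survival follow-up continues. The PFS clock then runs past progression to death or, if the patient is alive, to last contact. Both lengthen PFS. There is no control arm to share the error, because the comparator is a fixed median of 3 months, so the error acts only in favour of the treatment.

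**Working it through.** **1. Reasons for stopping, set against the schedules**

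| Reason for stopping durvalumab | 9.1.1 / 9.1.3 / 10.3.1 | 8.1.3 / 13.2 / appendix headings |
|---|---|---|
| Completed with disease control | CT continues | Appendix B (CT) |
| Toxicity, no confirmed progression | CT continues | Appendix B (CT) |
| Confirmed progression | not required | Appendix C (no CT) |
| New therapy, noncompliance, late-found ineligibility, pregnancy | CT continues, Appendix B | not assigned |
| Consent withdrawn | no observation (4.3) | no observation |

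Only the fourth row conflicts. Within it, a patient with a first, unconfirmed RECIST 1.1 progression already has a PFS event under Section 11.4. The patients at issue are those with no progression on any scan.

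**2. The plan's own figure**

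Inputs from Section 11.3: "We will use a 1-sided test with a 5% significance level", 80% power, "the median PFS is prolonged from 3 to 4.5 months", "we estimate an accrual time of 26 months for a total sample size of 39 patients", exponential survival. Section 11.2.2 gives 18 patients a year and 12 months of maturation.

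- Events: (1.645 + 0.842)² / [ln(3/4.5)]² = 37.6
- Probability of an event at median 4.5 months, with λ = ln 2/4.5: 1 − (e^(−12λ) − e^(−38λ))/(26λ) = 0.961
- N: 37.6/0.961 = 39.1, against the stated 39; accrual 18 × 26/12 = 39
- Power at 39: Φ(√(39 × 0.961) × 0.4055 − 1.645) = 79.9%

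The design is reproduced as a one-sample, one-sided exponential test.

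**3. Effect of unscanned patients under the null**

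Assumptions not in the documents:
- The number of unscanned patients.
- Time from progression to death is exponential with median 1.3 or 3.0 months. These are the differences between median OS and median PFS in the two arms of the second-line trial described in Section 1.1: 3.3 − 2.0 = 1.3 and 5.9 − 2.9 = 3.0.
- Every unscanned patient's PFS becomes progression time plus that residual.

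True median PFS is 3 months and follow-up is uniform between 12 and 38 months. With D events and E = (ln 2/3) × total PFS time, reject if −ln(D/E) × √D > 1.645.

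| Unscanned of 39 | Gap 1.3 months | Gap 3.0 months |
|---|---|---|
| 0 | 3.8% | 3.8% |
| 1 | 4.3% | 5.2% |
| 2 | 4.9% | 7.2% |
| 4 | 6.5% | 12.2% |

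These rows fix the number of unscanned patients exactly (100,000 simulated trials each). If each patient instead has that chance of being unscanned, so that the number varies around the same mean, the rates are slightly higher: 4.4% / 5.4%, 5.1% / 7.5% and 6.6% / 13.0%. With four expected, the null median PFS becomes 3.20 or 3.33 months. A one-sample log-rank test gives nearly the same rates.

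A PFS event that is itself a death does not move. If 20% of PFS events were deaths (assumed), four unscanned patients would give 5.8% or 10.1%.

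**The case against.** The strongest reply is that the documents already answer the question. The dedicated imaging section says these patients are scanned and names Appendix B, Section 9.1.3 repeats it, and Section 10.3.1 takes it for granted. No passage tells a site to stop CT in them; Sections 8.1.3 and 13.2 are silent about them rather than opposed. This stands as evidence of intent. A reader might infer that the plan drops CT for these patients, and the documents do not support that. What remains is that the schedules do not carry the intent through.

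A reader might also infer that footnote j of the Schedule of Study Assessments, which runs CT until progression or off-study, ends their scans. It governs on-treatment scans, and stopping durvalumab is not the same as leaving the study.

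The size rests on assumptions. The documents give no rate for these reasons, and nothing in them supports shares as high as 15-20% of patients, where simulated error rates become alarming. The model also assumes no clinically indicated scan, although Section 9.1.1 allows one, and a difference of medians is only a rough stand-in for survival after progression. Under Section 4.4 some early leavers may be replaced, though Section 11.2.2 keeps all patients entered in a strict intention-to-treat analysis. All of these limit the size; none reverses the direction.

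Finally, noncompliant patients may refuse visits, and a new heading will not bring them to the scanner. That stands, and it is why Section 11.4 needs a rule as well.

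**Conclusion.** The inconsistency is real and touches the primary endpoint. Patients who stop for the remaining Section 4.3 reasons are promised CT in one set of sections and left without a schedule in another. If the site follows the headings, their PFS can run to death or last contact, and the single-arm test is biased towards declaring benefit.

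The likely size is modest. Relative to about 4% with complete scanning, the null rejection rate is about 4-5% with one unscanned patient of 39, 5-7% with two and 6-12% with four, and lower if some PFS events are deaths. These figures rest on the assumed counts, the 1.3 to 3.0 month gap, and a complete absence of scans in those patients. They illustrate sensitivity and do not forecast the trial's error rate. The sample size of 39 is not in question.

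**What to change.** - In Sections 8.1.3 and 13.2, the Appendix B heading and the list of appendices, replace the limitation to toxicity with: *discontinued durvalumab for any reason other than confirmed PD*. Keep the word *confirmed*, so that Appendices B and C together cover everyone who stops and remains under observation, including a patient with a first, unconfirmed progression.
- In footnote j of the Schedule of Study Assessments, state that stopping durvalumab does not by itself end CT.
- In Section 11.4, censor patients without documented progression or death at their last evaluable tumor assessment instead of at last contact.

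The third edit acts only on patients still alive. In the simulation only about 2% (gap 1.3 months) to 5% (gap 3.0 months) of unscanned patients were alive at analysis, so keeping the scans does most of the work. Section 11.4 should also say how a death after a long gap in scanning is counted.

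The cost is wording, plus a few CTs that Section 9.1.1 already requires. Sample size and planned power are essentially unchanged.

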### **9.1.2 Definitions for Disease Assessment**

**Measurable lesions:** Lesions that can be accurately measured in at least one dimension with longest diameter at least 10 mm on CT scan.

**Malignant lymph nodes:** To be considered measurable, a lymph node must be at least 15 mm by CT scan.

**Non-measurable lesions:** All other lesions <10 mm on CT scan.

**Target lesions:** Target lesions should be identified and measured at baseline. Target lesions include measurable lesions up to a maximum of two lesions per organ and up to five lesions in total that are representative of all involved organs. Target lesions should be selected on the basis of their size (lesions with the longest diameter) and are to undergo reproducible repeated measurements. If the largest lesion does not lend itself to reproducible measurement it should not be considered a target lesion and instead the next largest lesion that can be measured reproducibly should be selected. A sum of the longest diameters for all target lesions will be calculated and reported as the baseline sum diameters. The baseline sum diameters will be used as reference to further characterize any objective tumor regression in the measurable dimension of the disease.

**Non-target Lesions:** All other lesions (or sites of disease) including any measurable lesions over and above the 5 target lesions should be identified as non-target lesions and should also be recorded at baseline. Measurements of these lesions are not required, but the presence, absence, or in rare cases unequivocal progression of each should be noted throughout follow-up.

### 9.1.3 Evaluation of Disease Response

Response assessment will be made using RECIST 1.1.

#### Definition of response in target lesions:

- **Complete Response (CR):** Disappearance of all target lesions
- **Partial Response (PR):** At least a 30% decrease in the sum of the diameters of target lesions, taking as reference the baseline sum diameters
- **Progressive Disease (PD):** At least a 20% increase in the sum of the diameters of target lesions compared to baseline sum of target lesions, or any new lesions
- **Stable Disease (SD):** Neither sufficient decrease to qualify as a PR or sufficient increase to qualify as PD

Response should be confirmed by repeat CT scan that may be performed at the next regularly scheduled scan and no earlier than 4 weeks after imaging showing a particular response (unless clinically indicated).

Definition of response in non-target lesions

- **Complete Response (CR):** Disappearance of all non-target lesions
- **Progressive Disease (PD):** Appearance of one or more new lesions and/or unequivocal progression of existing non-target lesions
- **Incomplete Response/Stable Disease (SD):** Persistence of one or more non-target lesions

The response to immunotherapy may differ from the typical responses observed with cytotoxic chemotherapy including the following (Wolchok, Hoos et al. 2009, Nishino, Giobbie-Hurder et al. 2013).

- Response to immunotherapy may be delayed
- Response to immunotherapy may occur after PD by conventional criteria
- The appearance of new lesions may not represent PD with immunotherapy
- SD while on immunotherapy may be durable and represent clinical benefit.

Based on the above-described unique response to immunotherapy and based on guidelines from regulatory agencies, e.g., European Medicines Agency's "Guideline on the evaluation of anti-cancer medicinal products in man" (EMA/CHMP/205/95/Rev.4) for immune modulating anti-cancer compounds, the following will be included in disease response evaluation in addition to standard RECIST 1.1 criteria:

- RECIST will be modified so that PD must be confirmed at the next scheduled visit, preferably, and no earlier than 4 weeks after the initial assessment of PD in the absence of clinically significant deterioration. Treatment with durvalumab would continue between the initial assessment of progression and confirmation for progression.

- In addition, subjects may continue to receive durvalumab beyond confirmed PD in the absence of clinically significant deterioration and if investigators consider that subjects continue to receive benefit from treatment.

Modification of RECIST as described may discourage the early discontinuation of durvalumab and provide a more complete evaluation of its anti-tumor activity than would be seen with conventional response criteria. Nonetheless, the efficacy analysis will be conducted by programmatically deriving each efficacy endpoint based on RECIST 1.1 criteria.

Of note, clinically significant deterioration is considered to be a rapid tumor progression that necessitates treatment with anti-cancer therapy other than durvalumab or with symptomatic progression that requires urgent medical intervention (e.g., central nervous system metastasis, respiratory failure due to tumor compression, spinal cord compression).

Subjects who have disease control following completion of 12 months of treatment or subjects who are withdrawn from durvalumab treatment for reasons other than confirmed PD will continue to have objective tumor assessments (see Appendix B).

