#### **9.1.4 Evaluation of Best Overall Response**

The best overall response is the best response recorded from the start of treatment until disease progression/recurrence.

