### **11.4 Efficacy Endpoints**

#### **Primary**

Clinical Study Protocol  
Investigational Drug Substance: MEDI4736  
Study Number **ESR 15 11078**  
Edition Number **1.09**  
Date **01 Feb 2018**

**Progression free survival (PFS):** Progression free survival is defined as the time from the initiation of durvalumab to the first documented disease progression per RECIST 1.1 or death due to any cause, whichever occurs first. If a patient recurs and is eligible for retreatment, then only the time to the initial recurrence will be included in the evaluation of PFS. Patients who are alive with no evidence of disease at the time of last contact will be censored at that date.

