### **Secondary**

**Overall Response Rate (ORR):** The overall response rate is defined as the percentage of the patients who have a complete response (CR) or partial response (PR) as defined by RECIST 1.1. The patient's best overall response rate defined as the best response recorded from the start of the treatment until disease progression will be recorded.

**Clinical Benefit Rate (CBR) –** The clinical benefit rate is the percentage of patients that have achieved a complete response, partial response, or stable disease as defined by RECIST 1.1.

**Time to in-field progression –** The time to in-field progression is defined as the time from initiation of treatment to progression of disease within the radiation field.

**Overall Survival –** Overall survival is defined as the time from first treatment until death. Patients who are alive will be censored at the last date of patient contact.

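### Target-lesion progression is written against the baseline sum, so after shrinkage the PFS event can be dated late and never early

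*Combined protocol and SAP*

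**What the plan says.** Section 9.1.3 names RECIST 1.1 as the response standard and then writes out its definitions. Progressive disease (PD) in target lesions is "At least a 20% increase in the sum of the diameters of target lesions compared to baseline sum of target lesions", or any new lesion. For non-target disease it is "Appearance of one or more new lesions and/or unequivocal progression of existing non-target lesions".

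Section 9.1.2 gives the baseline sum one role: "The baseline sum diameters will be used as reference to further characterize any objective tumor regression". It states no reference for growth, and no section mentions the smallest sum reached on study.

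Section 9.1.3 then adds a rule that PD be confirmed, but closes by saying that "the efficacy analysis will be conducted by programmatically deriving each efficacy endpoint based on RECIST 1.1 criteria". Section 11.4 dates PFS from the start of durvalumab to first documented progression per RECIST 1.1 or death. For retreated patients it adds that "only the time to the initial recurrence will be included in the evaluation of PFS". Section 9.1.4 defines best response as the "best response recorded from the start of treatment until disease progression/recurrence". The word recurrence is not defined, and the class of a target that reappears after complete response is not stated.

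**The concern.** Under the written rule the bar for sum-based progression stays at 120% of the baseline sum, however far the targets have shrunk. A patient whose targets fall and then clearly regrow can therefore stay progression-free on target measurements for one or more further scans.

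The matter is not remote in this design. Section 5.2 prefers the two largest eligible lesions for radiation, Section 9.1.2 picks target lesions by size, and no text keeps irradiated lesions out of the target set. Radiation is scheduled for Days 15-17 and 29-31, before the week 8 scan. Irradiated lesions may thus form part of the target sum, although the documents give no shrinkage rate.

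At stake is the date of the sole primary endpoint. The trial has one arm and a fixed 3-month benchmark, so no concurrent control shares a dating error. Two analysts could also derive different PFS dates from the same scans, one using the written line in 9.1.3 and the other the standard it names.

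**Working it through.** **Inputs.** PD threshold: 9.1.3. CT every 8 weeks, or sooner if clinically indicated: 9.1.1. Median PFS 3 versus 4.5 months, one-sided 5%, power 80%, N = 39, 26 months of accrual: 11.3. Accrual of 18 per year plus 12 months of maturation: 11.2.2. Model, from 11.3: "The method used for sample size estimation assumes exponential survival distributions".

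**1. The plan's own sample size.** Events = (1.645 + 0.842)² / (ln 1.5)² = 37.6. With uniform accrual over 26 months, 12 months more follow-up and a 4.5-month median, P(event) = 0.961. N = 37.6 / 0.961 = 39.1, and power at N = 39 is 79.9%. The figure reproduces, and it does not depend on the PD reference.

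**2. Regrowth needed.** If the sum has fallen by a fraction s, reaching 120% of baseline needs growth of 1.2/(1 − s) − 1 from the smallest sum:

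| Decrease | Growth needed, baseline reference | Growth needed, smallest-sum reference |
|---|---|---|
| 10% | 33% | 20% |
| 20% | 50% | 20% |
| 30% | 71% | 20% |
| 50% | 140% | 20% |

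**3. Direction and earliest date.** The smallest sum, baseline included, is never above the baseline sum. The baseline threshold is therefore never crossed first, and PFS can only stay the same or lengthen. At week 8 the only earlier scheduled sum is baseline, so the two rules agree. The first scheduled date on which they can differ is week 16 (112/30.4375 = 3.68 months). An unscheduled earlier scan could bring this forward.

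**4. Delay for one patient.** Growth rates are assumed, since the documents give none. The smallest sum is at week 8 and scans follow every 8 weeks:

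| Week 8 sum (baseline 100) | Growth per scan | PD, smallest sum | PD, baseline | Delay |
|---|---|---|---|---|
| 90 | 20% | week 16 | week 24 | 8 weeks |
| 80 | 20% | week 16 | week 32 | 16 weeks |
| 70 | 20% or 30% | week 16 | week 32 | 16 weeks |
| 70 | 50% | week 16 | week 24 | 8 weeks |
| 80 or 90 | 50% | week 16 | week 16 | none |

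Slow growth gives longer delays. From 70 at 10% per scan, 84 is passed at the 2nd further scan and 120 at the 6th, a delay of 4 × 8 = 32 weeks. All of these assume no new lesion, non-target progression or death in between.

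**5. Who could be affected.** Week 8 is 1.84 months. Event-free past week 8: 2^(−1.84/3) = 0.654, or 25.5 of 39, at a 3-month median; 2^(−1.84/4.5) = 0.753, or 29.4 of 39, at 4.5 months. These are upper bounds on scheduled scans. Only those among them whose targets shrank and then progressed by the sum alone can be dated late.

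**6. Sensitivity of the test, not an estimate.** Assume a true median of 3 months, a benchmark measured without the baseline reference, and an exponential log-hazard test (the documents name no statistic). Let a share of all events from week 16 on be dated late. Rejection rates from 60,000 simulated trials per scenario:

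| Share dated late | 8-week delay | 16-week delay |
|---|---|---|
| 0% | 3.9% | 3.8% |
| 10% | 5.0% | 6.5% |
| 20% | 6.2% | 10.2% |
| 30% | 7.7% | 14.6% |
| 50% | 12.0% | 26.2% |

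Nothing in the documents supports any particular row.

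**The case against.** The best reply is that a governing standard is already named. Section 9.1.3 ends by tying every efficacy endpoint to RECIST 1.1, and 11.4 dates PFS by it, so the baseline line could be read as a loose summary. This much stands: a reader might infer that no text governs, and that goes too far. But 9.1.3 introduces its definitions as RECIST 1.1, the baseline threshold is the only one written out, and nothing ranks it against the named standard.

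Several stronger readings are tempting and are not supported:

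- **That progression will be dated late.** It can be. Fast regrowth crosses both thresholds at the same scan, and other events still count.
- **That the error must favour treatment.** Longer observed PFS is arithmetic. Bias against the benchmark also requires that the cited second-line trial did not use the baseline reference, and the documents do not say how it measured progression.
- **That the response rate is inflated.** Best response closes at progression, so the reference matters in principle. But responses need a confirmatory scan, and 9.1.3 also has a PD-confirmation rule. Single-scan examples do not establish a change.
- **That a few deferred dates would move the median.** At a 3-month median, 39 × (0.654 − 0.427) = 8.8 events from all causes fall between weeks 8 and 16. Three of them would be 34%, and each would have to be purely sum-based after shrinkage and still below 120% of baseline. The documents offer no basis for that share.

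The undefined word recurrence is peripheral. In 11.4 it concerns retreated patients only, and the main PFS sentence already defines the event.

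**Conclusion.** The point holds in limited form and should be fixed. The written threshold uses the baseline sum, no smallest-sum reference exists, and the documents do not say whether that wording or the standard they name decides the PD date. After shrinkage the written rule can delay sum-based progression and cannot advance it, from week 16 on scheduled scans.

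Confidence is high on the text, the direction and the threshold arithmetic. It is low on the effect on PFS: the frequency of shrinkage, the pace of regrowth and the benchmark's own reference are all absent, so the change in the median and in type I error cannot be determined. The sample size of 39 is unaffected.

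**What to change.** In Section 11.4, state that for deriving PFS and best response:

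- target-lesion progression is an increase of at least 20% from the smallest target-lesion sum on study, baseline included;
- reappearance of target lesions after complete response is progression;
- the same event is meant where 11.4 speaks of recurrence;
- this text governs endpoint derivation over the baseline wording in 9.1.3.

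The sponsor should decide whether to add a minimum absolute increase. PD is also used for stopping durvalumab in Sections 4.3, 5.1.2 and 6.3. The sponsor should reconcile those sections with 9.1.3; no treatment rule is proposed here.

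The cost is a few sentences and the matching derivation code, with no extra scans, measurements or patients. PFS may look slightly shorter. Without a minimum increase, small growth from a very small sum would count: from 10 mm, 2 mm is already 20%. If the benchmark did use the baseline reference, the change would make the comparison somewhat conservative, so the report should state the reference used.
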